6.3.1.1 Adverse events after the 30 day follow-up period

For pharmacovigilance purposes and characterization, any case of MDS/AML or new primary malignancy occurring after the 30 day follow-up period should be reported to the AstraZeneca Safety Representative whether it is considered a non-serious adverse event (e.g., non-melanoma skin cancer) or an SAE, and regardless of the Investigator's assessment of causality. Investigators will be asked during the regular follow-up for survival if the subject has developed MDS/AML or a new primary malignancy, and will be prompted to report any such cases.

At any time after a subject has completed the study (i.e., no longer receiving study drug and past the 30 day follow-up period), if an Investigator learns of any SAE, including sudden death of unknown cause, and he/she considers there is a reasonable possibility that the event is causally related to olaparib, the Investigator should notify the AstraZeneca Safety Representative.

Otherwise, after study treatment completion (i.e., after any scheduled post-treatment follow-up period has ended), there is no obligation to actively report information on new adverse events or SAEs occurring in former study subjects.

6.3.2 Follow-up of unresolved adverse events

Any SAE or non-serious adverse event that is ongoing at the time of the 30-day follow-up, must be followed-up to resolution, until the condition stabilizes, is judged by the Investigator to be no longer clinically significant, or until the subject is lost to follow-up. AstraZeneca retains the right to request additional information for any subject with ongoing adverse event(s)/SAE(s) at the end of the study, if judged necessary.

6.3.3 Variables

The following variables will be collected for each adverse event:

- Adverse event (verbatim),
- The date when the adverse event started and stopped,
- CTCAE grade and changes in CTCAE grade,
- Whether the adverse event is serious or not,
- Investigator causality rating against olaparib (yes or no),
- Action taken with regard to olaparib,
- Outcome, and
- Adverse event caused subject's withdrawal from study (yes or no).

In addition, the following variables will be collected for SAEs:

- Date adverse event met criteria for an SAE,
- Date Investigator became aware of an SAE,
- Adverse event is serious due to,
- Date of hospitalization,
- Date of discharge,
- Probable cause of death,
- Date of death,
- Autopsy performed,
- Causality assessment in relation to study procedure(s),

- Causality assessment in relation to other medication, and
- Description of adverse event.

Severity of adverse event

For each episode of an adverse event, all changes to the CTCAE grade attained, as well as the highest attained CTCAE (version 4.03) grade, should be reported.

It is important to distinguish between serious and severe adverse events. Severity is a measure of intensity whereas seriousness is defined by the criteria in Section 6.2. An adverse event of severe intensity need not necessarily be considered serious. For example, nausea that persists for several hours may be considered severe nausea but not an SAE unless it meets the criteria shown in Section 6.2. On the other hand, a stroke that results in only a limited degree of disability may be considered a mild stroke, but would be an SAE when it satisfies the criteria shown in Section 6.2.

The grading scales found in the National Cancer Institute (NCI) CTCAE version 4.03 will be utilized for all events with an assigned CTCAE grading. For those events without assigned CTCAE grades, the recommendation is that the CTCAE criteria that convert mild, moderate, and severe events into CTCAE grades should be used.

A copy of the CTCAE version 4.03 can be downloaded from the Cancer Therapy Evaluation Program website (http://ctep.cancer.gov).

6.3.4 Causality collection

The Investigator will assess causal relationship between olaparib and each adverse event, and answer 'yes' or 'no' to the question 'Do you consider that there is a reasonable possibility that the event may have been caused by the investigational product?'

For SAEs, causal relationship will also be assessed for other medications and study procedures. Note: For SAEs that could be associated with any study procedure, the causal relationship is implied as 'yes.'

A guide to the interpretation of the causality question is found in Appendix A to the Clinical Study Protocol.

6.3.5 Adverse events based on signs and symptoms

All adverse events spontaneously reported by the subject or reported in response to the open question from the study personnel: *'Have you had any health problems since the previous visit/you were last asked?,'* or revealed by observation, will be collected and recorded in the eCRF. When collecting adverse events, the recording of diagnoses is preferred (when possible) to recording a list of signs and symptoms. However, if a diagnosis is known and there are other signs or symptoms that are not generally part of the diagnosis, the diagnosis and each sign or symptom will be recorded separately.

6.3.6 Adverse events based on examinations and tests

The results from protocol-mandated laboratory tests and vital signs will be summarized in the CSR. Deterioration as compared to baseline in protocol-mandated laboratory values, vital signs, and ECG abnormalities should therefore only be reported as adverse events if 1 of the following is met:

- Any criterion for an SAE is fulfilled,
- Causes study treatment discontinuation,
- Causes study treatment interruption,
- Causes study treatment dose reduction, or
- The Investigator believes that the abnormality should be reported as an adverse event.

If deterioration in a laboratory value/vital sign is associated with clinical signs and symptoms, the sign or symptom will be reported as an adverse event, and the associated laboratory result/vital sign will be considered as additional information. Wherever possible, the reporting Investigator should use the clinical, rather than the laboratory term (e.g., anemia versus low hemoglobin value). In the absence of clinical signs or symptoms, clinically relevant deteriorations in non-mandated parameters should be reported as adverse event(s).

Deterioration of a laboratory value, which is unequivocally due to disease progression, should not be reported as an adverse event/SAE.

Any new or aggravated clinically relevant abnormal medical finding at a physical examination, as compared with the baseline assessment, will be reported as an adverse event.

6.3.7 Hy's Law

Potential Hy's Law cases where a subject shows elevations in liver biochemistry may require further evaluation and occurrences of AST or $ALT \ge 3 \times ULN$ together with $TBL \ge 2 \times ULN$ and may need to be reported as SAEs. Confirmed Hy's Law cases should always be reported as SAEs. Please refer to Appendix D for further instruction on cases of increases in liver biochemistry and evaluation of Hy's Law.

6.3.8 Disease progression

Disease progression can be considered as a worsening of a subject's condition attributable to the disease for which olaparib is being studied. It may be an increase in the severity of the disease under study and/or increases in the signs and symptoms of the cancer. The development of new, or progression of existing metastasis to the primary cancer under study should be considered as disease progression and not an adverse event. Events which are unequivocally due to disease progression should not be reported as adverse events during the study.

For this study, objective radiological disease progression will be determined as per RECIST v1.1. See Appendix G.

6.3.9 New cancers

The development of a new primary cancer (including skin cancer) should be regarded as an adverse event (see Section 6.1.1 Olaparib Adverse Events of Special Interest). New primary malignancies are those that are not the primary reason for the administration of the study treatment and have developed after the inclusion of the subject into the study. They do not include metastases of the original cancer. Symptoms of metastasis or the metastasis itself should not be reported as an adverse event/SAE, as they are considered to be disease progression.

6.3.10 Lack of efficacy

When there is deterioration in the cancer for which the study treatment(s) is being used, there may be uncertainty as to whether this is lack of efficacy or an adverse event. In such cases, unless the Sponsor or the reporting physician considers that the study treatment contributed to the deterioration of the condition, the deterioration should be considered to be a lack of efficacy and not an adverse event.

6.3.11 Deaths

All deaths that occur during the study or within the protocol-defined 30-day follow-up period after the administration of the last dose of study treatment, must be reported as follows:

- Death that is clearly the result of disease progression should be reported to the study monitor at the next monitoring visit and should be documented in the death eCRF, but should not be reported as an SAE.
- Where death is not due (or not clearly due) to progression of the disease under study, the adverse event causing the death must be reported to the AstraZeneca Safety Representative as an SAE within 24 hours (see Section 6.4 for further details). The report should contain a comment regarding the co-involvement of progression of disease, if appropriate, and should assign main and contributory causes of death. This information can be captured in the death eCRF.
- Deaths with an unknown cause should always be reported as SAEs. A post-mortem evaluation may be helpful in the assessment of the cause of death, and if performed, a copy of the post-mortem results should be forwarded to the AstraZeneca Safety Representative within the usual timeframes.

6.4 **Reporting of serious adverse events**

All SAEs have to be reported, whether or not considered causally related to olaparib or to the study procedure(s). All SAEs will be recorded in the eCRF. See Section 6.3 for adverse event recording information.

If any SAE occurs in the course of the study, then Investigators or other site personnel will inform the appropriate AstraZeneca Safety Representatives **within 1 day**, i.e., immediately, but **no later than 24 hours** of when he or she becomes aware of it.

The designated AstraZeneca Safety Representatives will work with the Investigator to ensure that all the necessary information is provided to the AstraZeneca data entry site within **1 calendar day** of initial receipt for fatal and life-threatening events **and within 5 calendar days** of initial receipt for all other SAEs.

For fatal or life-threatening adverse events where important or relevant information is missing, active follow-up is undertaken immediately. Investigators or other site personnel will inform AstraZeneca Safety Representatives of any follow-up information on a previously reported SAE within 1 calendar day, i.e., immediately, but no later than 24 hours of when he or she becomes aware of it.

Once the Investigators or other site personnel indicate an adverse event is serious in the EDC system, an automated email alert is sent to the designated AstraZeneca Safety Representative.

If the EDC system is not available, then the Investigator or other study site personnel will report an SAE to the appropriate AstraZeneca Safety Representative by telephone. If the eCRF is not available, paper back-up forms should be used (including SAE, pregnancy, and overdose forms).

The AstraZeneca Safety Representative will advise the Investigator/study site personnel how to proceed.

Safety Contact Information: Medpace Clinical Safety

Medpace SAE hotline – USA: [contact], [name] or [contact], [name] [contact] or [contact] e-mail: [contact]

6.5 Overdose

There is currently no specific treatment in the event of overdose with olaparib and possible symptoms of overdose are not established.

Olaparib must only be used in accordance with the dosing recommendations in this protocol. Any dose or frequency of dosing that exceeds the dosing regimen specified in this protocol should be reported as an overdose. The maximum tolerated dose is 300 mg *bid* (tablet).

Adverse reactions associated with overdose should be treated symptomatically and should be managed appropriately.

- An overdose with associated adverse events is recorded as the adverse event diagnosis/symptoms on the relevant adverse event modules in the eCRF and on the Overdose eCRF module.
- An overdose without associated symptoms is only reported on the Overdose eCRF module.

If an overdose on an AstraZeneca study medication occurs in the course of the study, then the Investigator or other site personnel will inform appropriate AstraZeneca Safety Representatives immediately, or **no later than 24 hours** of when he or she becomes aware of the overdose.

The designated AstraZeneca Safety Representative works with the Investigator to ensure that all relevant information is provided to the AstraZeneca Representative data entry site.

For overdoses associated with an SAE, the standard reporting timelines apply; see Section 6.4. For other overdoses, reporting must occur **within 30 days**.

6.6 Pregnancy

All pregnancies and outcomes of pregnancy should be reported to the AstraZeneca Safety Representative.

6.6.1 Maternal exposure

If a subject becomes pregnant during the course of the study, olaparib should be discontinued immediately.

[figure not shown]
The outcomes of any conception occurring from the date of the first dose of study medication until 1 month after the last dose of study medication must be followed-up and documented.

Pregnancy itself is not regarded as an adverse event unless there is a suspicion that the olaparib under study may have interfered with the effectiveness of a contraceptive medication. Congenital abnormalities/birth defects and spontaneous miscarriages should be reported and handled as SAEs. Elective abortions without complications should not be handled as adverse events. The outcome of all pregnancies (spontaneous miscarriage, elective termination, ectopic pregnancy, normal birth, or congenital abnormality) should be followed-up and documented even if the subject was discontinued from the study.

If any pregnancy occurs in the course of the study, then the Investigator or other site personnel will inform the appropriate AstraZeneca Safety Representatives **within 1 day**, i.e., immediately, but **no later than 24 hours** of when he or she becomes aware of the pregnancy.

The designated AstraZeneca Safety Representative works with the Investigator to ensure that all relevant information is provided to the AstraZeneca data entry site within 1 or 5 calendar days for SAEs (see Section 6.4) and within 30 days for all other pregnancies.

The same timelines apply when outcome information is available.

Clinical Study Protocol Drug Substance Olaparib Study Code D0816L00003 Version 3.0 Date 10 October 2017			
			1

If a subject experiences a dose interruption > 4 weeks, the subject cannot restart study medication. See Section 6.7.

Common treatable causes of anemia (e.g., iron, vitamin B12, or folate deficiencies and hypothyroidism) should be investigated and appropriately managed. In some cases, management of anemia may require blood transfusions. For cases where subjects develop prolonged hematological toxicity (≥ 2 week interruption/delay in study treatment due to CTCAE grade 3 or worse anemia and/or development of blood transfusion dependence), refer to Section 6.7.1.3.

Clinical Study Protocol Drug Substance Olaparib Study Code D0816L00003 Version 3.0 Date 10 October 2017		
CCI		

If a subject experiences a dose interruption > 4 weeks the subject cannot restart study medication. See Section 6.7.

Adverse events of neutropenia and leukopenia should be managed as deemed appropriate by the Investigator with close follow-up and interruption of study medication if CTCAE grade 3 or worse neutropenia occurs.

Primary prophylaxis with Granulocyte colony-stimulating factor (G-CSF) is not recommended; however, if a subject develops febrile neutropenia, study treatment should be stopped and appropriate management including G-CSF should be given according to local hospital guidelines. Please note that G-CSF should not be used within at least 24 hours (7 days for PEGylated G-CSF) of the last dose of study treatment unless absolutely necessary.

Platelet transfusions, if indicated, should be done according to local hospital guidelines.

For cases where subjects develop prolonged hematological toxicity (≥ 2 week interruption/delay in study treatment due to CTCAE grade 3 or worse), refer to Section 6.7.1.3.

6.7.1.3 Management of prolonged hematological toxicities while on study treatment

If a subject develops prolonged hematological toxicity such as:

- ≥ 2 week interruption/delay in study treatment due to CTCAE grade 3 or worse anemia and/or development of blood transfusion dependence,
- \geq 2 week interruption/delay in study treatment due to CTCAE grade 3 or worse neutropenia (ANC < 1 × 10⁹/L), or
- ≥ 2 week interruption/delay in study treatment due to CTCAE grade 3 or worse thrombocytopenia and/or development of platelet transfusion dependence (platelets < 50 × 10⁹/L).

Check weekly differential blood counts including reticulocytes and peripheral blood smear. If any blood parameters remain clinically abnormal after 4 weeks of dose interruption, the subject should discontinue olaparib treatment and be referred to hematologist for further investigations. Bone marrow analysis and/or blood cytogenetic analysis should be considered at this stage according to standard hematological practice. Study treatment should be discontinued if blood counts do not recover to CTCAE grade 1 or better within 4 weeks of dose interruption.

Development of a confirmed MDS/AML or other clonal blood disorder should be reported as an SAE, and full reports must be provided by the Investigator to the AstraZeneca Safety Representative. Olaparib treatment should be discontinued if a subject's diagnosis of MDS and/or AML is confirmed.

If a subject experiences a dose interruption > 4 weeks the subject cannot restart study medication. See Section 6.7.

6.7.2 Management of non-hematological toxicity

Repeat dose interruptions are allowed as required, for a maximum of up to 4 weeks on each occasion. If the interruption is longer than 4 weeks, the AstraZeneca Representative Study Physician must be informed. See Section 6.7. When the toxicity reoccurs following re-challenge with study treatment, and where further dose interruptions are considered inadequate for management of toxicity, then the subject should be considered for dose reduction or must permanently discontinue study treatment.

CCI

Treatment must be interrupted if any NCI-CTCAE grade 3 or 4 adverse event occurs, which the Investigator considers to be related to administration of study treatment.

6.7.2.1 Management of new or worsening pulmonary symptoms

If new or worsening pulmonary symptoms (e.g., dyspnea) or radiological abnormalities occur in the absence of a clear diagnosis, an interruption in study treatment dosing is recommended and further diagnostic workup (including a high resolution CT scan) should be performed to exclude pneumonitis.

Following investigation, if no evidence of abnormality is observed on CT imaging and symptoms resolve, then study treatment can be restarted, if deemed appropriate by the Investigator. If significant pulmonary abnormalities are identified, these need to be discussed with the AstraZeneca Representative Study Physician.

If a subject experiences a dose interruption > 4 weeks the subject cannot restart study medication. See Section 6.7.

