follow-up (see Section 6.3.2). All new adverse events and SAEs occurring during the 30 calendar days after the last dose of study medication must be reported (if SAEs, they must be reported to AstraZeneca Safety representative **within 24 hours** as described in Section 6.4) and followed to resolution as above. Subjects should be seen at least 30 days after discontinuing study medication to collect and/or complete adverse event information. For guidance on reporting adverse events after the 30 day follow-up period see Section 6.3.1.1.

All subjects who received at least 1 dose of olaparib must be followed for progression and survival through the final analysis of all primary and secondary endpoints (approximately 6 months after the last subject has commenced study treatment [received at least 1 dose of olaparib]) + an additional 12 months after the data cut-off for follow-up for survival for applicable subjects. At the end of this additional 12 months of survival follow-up, updated OS and safety analyses will be conducted and the study will be closed. Subjects are, however, permitted to continue to receive olaparib beyond the closure of the database if, in the opinion of the Investigator, they are continuing to receive benefit from treatment with olaparib. During this time, adverse events of special interest and SAEs must still be collected and reported until 30 days after the subject finally stops taking olaparib. See Section 4.3.

If a subject is withdrawn from the study, see Section 3.10. See Section 3.10.2 for details on subject replacement.

For information regarding the withdrawal of consent for donated biological samples, see Section 5.6.9.

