6.7.2.4 Interruptions for intercurrent non-toxicity related events

Study treatment dose interruption for conditions other than toxicity resolution should be kept as short as possible. If a subject cannot restart study treatment within 4 weeks for resolution of intercurrent conditions not related to disease progression or toxicity, the case should be discussed with the AstraZeneca Representative Study Physician. See Section 6.7.

All dose reductions and interruptions (including any missed doses), and the reasons for the reductions/interruptions, are to be recorded in the eCRF.

Study treatment should be stopped at least 3 days prior to planned surgery. After surgery, study treatment can be restarted when the wound has healed. No stoppage of study treatment is required for any needle biopsy procedure.

Study treatment should be discontinued for a minimum of 3 days before a subject undergoes palliative radiation treatment. Study treatment should be restarted within 4 weeks as long as any bone marrow toxicity has recovered.

[figure not shown]
Because the adverse events related to olaparib may include asthenia, fatigue, and dizziness, subjects should be advised to use caution while driving or using machinery if these symptoms occur.

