Palliative radiotherapy may be used for the treatment of pain at the site of bony metastases that were present at baseline, provided the Investigator does not feel that these are indicative of clinical disease progression during the study period. Study treatment should be discontinued for a minimum of 3 days before a subject undergoes therapeutic palliative radiation treatment. Study treatment should be restarted within 4 weeks as long as any bone marrow toxicity has recovered (i.e., if a subject has not recovered from bone marrow toxicity within 4 weeks they should be discontinued from the study).

Administration of other anti-cancer agents

Subjects must not receive any other concurrent anti-cancer therapy, including investigational agents, while on study treatment. Subjects may continue the use of bisphosphonates or denosumab for bone disease and corticosteroids for the symptomatic control of brain metastases provided the dose is stable before and during the study and they were started at least 4 weeks prior to beginning study treatment.

Subsequent therapies for cancer

Details of first and subsequent therapies for cancer and/or details of surgery for the treatment of the cancer, after discontinuation of treatment, will be collected until database lock for ORR. Reasons for starting subsequent anti-cancer therapies, including access to other PARP inhibitors or investigational drugs, will be collected until database lock for ORR.

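### Marrow toxicity not recovered at 4 weeks stops olaparib in Section 6.7.1.3 but ends study participation in Section 7.7; Sections 6.7.2 and 6.7.2.1 also differ on pulmonary holds over 4 weeks

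*Protocol*

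**What the plan says.** **Unrecovered marrow toxicity.** Section 6.7.1.3 (prolonged hematological toxicity) states: "Study treatment should be discontinued if blood counts do not recover to CTCAE grade 1 or better within 4 weeks of dose interruption". Section 7.7, in its text on palliative radiotherapy, states: "if a subject has not recovered from bone marrow toxicity within 4 weeks they should be discontinued from the study". Section 6.7.2.4 repeats the radiotherapy instruction (restart inside 4 weeks provided the marrow has recovered) but gives no consequence if it has not.

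**Follow-up.** Section 3.9.1 moves a subject who stops treatment into follow-up and adds: "All subjects who received at least 1 dose of olaparib must be followed for progression and survival through the final analysis". Section 4.4 applies survival follow-up to everyone dosed. Section 5.1.1 continues RECIST assessments to progression whatever happens to treatment. Section 3.10 lists four reasons for leaving the study: the subject's own choice, incorrect enrollment, loss to follow-up and death.

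**Interruptions longer than 4 weeks.** The hematological text printed ahead of Section 6.7.1.3 states: "If a subject experiences a dose interruption > 4 weeks, the subject cannot restart study medication". Section 6.7.1.3 carries the same bar, and so does Section 6.7.2.1 on pulmonary symptoms: "If a subject experiences a dose interruption > 4 weeks the subject cannot restart study medication". Section 6.7.2, the parent of 6.7.2.1, limits each interruption to 4 weeks and then says: "If the interruption is longer than 4 weeks, the AstraZeneca Representative Study Physician must be informed". Section 6.7.2.4 has a separate provision for conditions unrelated to progression or toxicity: "If a subject cannot restart study treatment within 4 weeks for resolution of intercurrent conditions", the case goes to the study physician for discussion. On surgery the same section says: "After surgery, study treatment can be restarted when the wound has healed".

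**The concern.** The protocol treats stopping olaparib (Section 3.9) and leaving the study (Section 3.10) as different events with different consequences for the data. A subject who only stops olaparib is still scanned to progression and followed for survival. A subject taken out of the study may be neither. Section 7.7 uses the second form of words for a finding that Section 6.7.1.3 handles with the first.

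A site that follows Section 7.7 as written would end follow-up because the marrow did not recover on treatment. The resulting censoring would be related to tolerability, and so possibly to prognosis. Kaplan-Meier estimates assume that it is not.

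The second pair matters less for the estimates. For a pulmonary hold beyond 4 weeks, a site reading the parent section sees a duty to notify, and a site reading the subsection sees a bar on restart. Exposure and the reported discontinuation rate could then depend on which section was consulted.

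**Working it through.** No figure in the plan bears on this point, so the check is a comparison of text.

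**Step 1. Set out each rule by cause.**

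| Cause of the hold | Section | Consequence after 4 weeks | Refers to Section 6.7? |
|---|---|---|---|
| Hematological toxicity | text ahead of 6.7.1.3 | no restart | yes |
| Prolonged hematological toxicity | 6.7.1.3 | olaparib stopped; no restart | yes |
| Non-hematological toxicity, general | 6.7.2 | physician told; 4-week maximum per occasion | yes |
| Pulmonary symptoms | 6.7.2.1 | no restart | yes |
| Conditions unrelated to progression or toxicity | 6.7.2.4 | case discussed with physician | yes |
| Palliative radiotherapy, marrow not recovered | 6.7.2.4 | none stated | not in the radiotherapy text |
| Palliative radiotherapy, marrow not recovered | 7.7 | subject leaves the study | no |

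**Step 2. Look for overlaps.** Most rows concern different causes and do not meet. Two pairs do.

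- *6.7.1.3 and 7.7.* Both address marrow or blood counts not recovered at 4 weeks. One ends treatment and the other ends study participation. The radiotherapy text in 7.7 does not point to Section 6.7.
- *6.7.2 and 6.7.2.1.* A pulmonary hold is a non-hematological hold, so both apply. Telling the physician and barring restart can both be done, but only the subsection states the bar.

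**Step 3. Test Section 7.7 against the follow-up rules.** Sections 3.9.1, 4.4 and 5.1.1 contain no exception for subjects stopped after radiotherapy. Unrecovered marrow is not among the four reasons in Section 3.10. Section 7.7 therefore stands alone.

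**Step 4. Trace a literal reading of Section 7.7 through the endpoint definitions.**

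- PFS (8.4.3.4) is meant to run regardless of withdrawal from therapy. Without further scans, a subject not known to have progressed or died is censored at the last evaluable assessment.
- DoR (8.4.3.1) takes over the PFS censoring time for a responder who has not progressed.
- OS (8.4.3.6) is censored at the last date known alive. Sections 3.10.2 and 4.4 allow vital status to be obtained from public sources, so the effect on OS is possible but not certain.

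**Step 5. Size.** The number affected is the number who receive palliative radiotherapy on study and whose marrow has not recovered within 4 weeks. The protocol gives neither frequency. Section 7.7 limits such radiotherapy to pain from bony metastases present at baseline, so the number is probably small. It cannot be estimated from the document.

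**The case against.** The strongest defence is that Section 7.7 contains one loosely worded parenthesis about a narrow situation. The follow-up duties are explicit in three other sections, and a careful site would keep following the subject. That reading is reasonable and limits the likely harm. It does not remove the conflict, because the site must still set aside the plain words of Section 7.7.

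For the second pair, the defence is that notification is compatible with a bar on restart, that Section 6.7.2 itself sets a 4-week maximum, and that the sections on interruption refer to Section 6.7, whose body is unreadable here. This largely stands. Section 6.7 may contain the governing rule.

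A reader might infer three stronger points, which the document does not support.

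- *That one and the same hold could end treatment, permit restart or end follow-up.* The rules attach to different causes. The discussion provision in Section 6.7.2.4 expressly excludes toxicity, and Section 7.7 is triggered by unrecovered marrow after radiotherapy, not by any long hold.
- *That restart after more than 4 weeks is permitted somewhere.* No visible passage clearly says so. Informing or consulting a physician grants nothing. The surgery sentence gives no time limit of its own, but it sits in a section that asks for short interruptions and refers those beyond 4 weeks to the study physician.
- *That the objective response rate would shift by a stated amount.* Section 8.4.2 counts confirmed responses up to progression, excludes those after further anti-cancer therapy, and does not require the subject to be on olaparib. Stopping treatment alone therefore does not remove a response. Any figure would also need an assumed rate of long holds, most of which are hematological or non-toxicity holds that the visible text treats consistently.

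**Conclusion.** The point holds in two limited parts. The conflict between Section 7.7 and Sections 6.7.1.3, 3.9.1, 3.10, 4.4 and 5.1.1 is established on the visible text and does not depend on the redacted material. If Section 7.7 is applied literally, PFS and DoR, and possibly OS, lose follow-up for a tolerability-related reason, in what is probably a small number of subjects. The difference between Sections 6.7.2 and 6.7.2.1 is an inconsistency of wording that Section 6.7 may already resolve. Neither part undermines the primary analysis, and no numerical size can be given. The conclusion on follow-up assumes that sites would read leaving the study in the sense of Section 3.10. It takes no view on when treatment should stop or restart.

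**What to change.** 1. Reconcile Section 7.7 with Sections 6.7.1.3, 6.7.2.4, 3.9.1, 3.10, 4.4 and 5.1.1. The text should make clear whether treatment or study participation ends when marrow has not recovered after palliative radiotherapy, and that the progression and survival follow-up required for all treated subjects still applies.
2. Reconcile Sections 6.7.2, 6.7.2.1 and 6.7.2.4 with Section 6.7, so that the consequence of an interruption longer than 4 weeks is stated once. Where it differs by cause, including after surgery, the text should say so.

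The sponsor decides which clinical rule holds. The cost is protocol wording only, with no added subjects, visits or procedures.
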